After completing your protocol, right click on the Table of Contents below and select “Update Field.” If prompted, select “Update entire table.” This will automatically update the protocol sections and page numbers for you. Do this also each time you modify your protocol after initial approval.

1.0	Objectives	7
2.0	Background	7
3.0	Study Endpoints/Events/Outcomes.....	10
4.0	Study Intervention(s)/Investigational Agent(s).....	10
5.0	Procedures Involved.....	11
6.0	Data and Specimen Banking.....	13
7.0	Sharing of Results with Participants	14
8.0	Study Duration.....	14
9.0	Study Population.....	14
10.0	Vulnerable Populations	15
11.0	Local Number of Participants	16
12.0	Local Recruitment Methods.....	16
13.0	Withdrawal of Participants	16
14.0	Risks to Participants.....	17
15.0	Potential Benefits to Participants	18
16.0	Data Management	18
17.0	Confidentiality	18
18.0	Provisions to Monitor the Data to Ensure the Safety of Participants	19
19.0	Provisions to Protect the Privacy Interests of Participants	19
20.0	Compensation for Research-Related Injury.....	19
21.0	Consent Process	19
22.0	Setting	20
23.0	Multi-Site Research: N/A	20
24.0	Resources Available.....	20
25.0	References.....	20

ABBREVIATIONS/DEFINITIONS

- CO – carbon monoxide
- FDA – Food and Drug Administration
- FSPTCA - Family Smoking Prevention and Tobacco Control
- E-Cig – E-Cigarette

STUDY SUMMARY

Study Title	Effect of Banning Menthol Flavorant on Cigarette and E-Cigarette Use
Study Design	Randomized Study
Primary Objective	To obtain preliminary information regarding how a menthol ban that either exempts or includes e-cigarettes is likely to affect overall tobacco use
Research Intervention(s)/Investigational Agents	Smokers of menthol cigarettes will be randomized to one of three experimental marketplace conditions: 1) a simulated ban on menthol cigarettes but not e-cigarettes; 2) a simulated ban on both menthol cigarettes and e-cigarettes and 3) no menthol ban for either product
IND/IDE # (if applicable)	n/a
Investigational Drug Services # (if applicable)	n/a
Study Population	Medically stable smokers
Sample Size (number of participants)	60
Study Duration for Individual Participants	Approximately 8 weeks

1.0 Objectives

1.1 Objective: The objective of this study is to obtain preliminary information regarding how a menthol ban that either exempts or includes e-cigarettes is likely to affect overall tobacco use

1.2 Specific Aims: The following specific aims will be pursued:

Aim 1: Determine the impact of the availability of menthol flavor in e-cigarettes on overall tobacco product use patterns

We hypothesize that menthol cigarette smokers will smoke fewer cigarettes, vape more e-cigarettes, have higher motivation to quit smoking and be more supportive of a ban on menthol cigarettes when given the option of using menthol flavored e-cigarettes than when no such option is present.

Aim 2: Determine if the impact of the availability of menthol flavor in e-cigarettes on tobacco use behavior is moderated by a ban on menthol flavor in cigarettes

We hypothesize that the impact of menthol flavored e-cigarette availability on the above measures will be greater during a simulated ban on menthol cigarettes than if smokers can continue smoking menthol cigarettes.

2.0 Background

2.1 *Significance of Research Question/Purpose:* With the passage of the Family Smoking Prevention and Tobacco Control Act (FSPTCA), the United States Food and Drug Administration (FDA) acquired broad ability to regulate tobacco products, which included the use of flavorants in cigarettes. In 2009, the FDA banned cigarettes flavored with fruit or candy in response to evidence that such flavoring encourages experimentation by young people and leads to regular use and ultimately addiction.¹ Menthol was specifically excluded from this ban as the FDA examines the role of menthol in initiation, maintenance, and health risks associated with the use of such products.¹ The Tobacco Products Scientific Advisory Committee in a report reviewing the impact of the use of menthol cigarettes to public health, provided the overall recommendation that “Removal of menthol cigarettes from the marketplace would benefit public health in the United States.”^{2,3} A report produced by the FDA evaluating the public health effects of menthol in cigarettes similarly concluded that menthol use is likely associated with increased smoking initiation by youth and young adults, that menthol in cigarettes is likely associated with greater addiction, and that menthol smokers are less likely to successfully quit smoking. Overall, this report concluded that it is “likely that menthol cigarettes pose a public health risk above that seen with non-menthol cigarettes.”⁴ The role of menthol flavoring in other tobacco products was not addressed in either of these reports.

The use of electronic nicotine delivery devices (e-cigarettes) has increased dramatically since their introduction in the United States in 2007. Recent surveys

have found that over 12% of adults have tried e-cigarettes and that 5.5% of all adults and 8.9% of young adults use e-cigarettes either every day or on some days.^{5, 6} Sales of e-cigarettes for 2016 are estimated at approximately \$1.6 billion and some estimates project that e-cigarette sales may overtake cigarette sales within 10 years.^{7, 8} Almost every commonly used brand of e-cigarette is currently available in menthol flavor⁹ and data from surveys suggest that as many as 30% of e-cigarette users prefer menthol flavored products with over 12% of e-cigarette users stating that they use e-cigarettes “because they come in menthol flavor.”¹⁰⁻¹³ However, there is little information assessing if the availability of menthol flavorant in e-cigarettes affects smoking behavior in the context of a ban on menthol flavorant in cigarettes.

With the recent extension of FDA authority to additional categories of tobacco products including e-cigarettes,¹⁴ the ability to enact regulations regarding the availability of flavorants (including menthol) will extend to these other categories of tobacco products as well. Although surveys of menthol smokers suggest that a substantial number would attempt to quit smoking if menthol cigarettes were unavailable,^{3, 15, 16} our preliminary data found that relatively few in fact made a cessation attempt (only 3 out of 31 subjects). However, it is not known if access to menthol flavored e-cigarettes would increase the likelihood of menthol smokers quitting smoking entirely in the event of a ban since they have an alternate menthol product available or conversely if likelihood of quitting would decrease with smokers opting to use a combination of non-menthol cigarettes and menthol flavored e-cigarettes. The former would support exempting menthol e-cigarettes from a menthol ban whereas the latter would support enacting a menthol ban that would include all tobacco products. Among the numerous research needs regarding e-cigarettes identified in an NIH sponsored workshop are the needs to evaluate the effects of flavorants, biomarkers of exposure, and patterns of use.¹⁴ The purpose of the current study is to obtain initial data regarding how menthol flavoring in e-cigarettes affects tobacco use patterns in menthol cigarette smokers in order to plan future studies that more definitely assess if regulatory policy regarding menthol flavoring should be uniform across products.

2.2 Preliminary Data: Our research team has considerable experience with the methods proposed in this study and with the study population being recruited. The most relevant projects include:

2.2.1 Data demonstrating that in the event of a menthol ban in cigarettes, smokers of menthol cigarettes switch to smoking non-menthol cigarettes: In a pilot study led by [name], we asked African American menthol cigarette smokers to not smoke menthol cigarettes for a 4 week period in order to obtain information regarding how they would adjust their smoking behavior were menthol cigarettes not available (as in the event of a ban).¹⁷ No specific instructions were provided regarding how to cope with abstaining from menthol cigarettes. Of the 32 subjects who completed the study, three reported making a quit attempt with all continuing smokers switching to non-menthol cigarettes. Modest decreases occurred in cigarettes smoked per day (11.9 vs. 9.8 cigs/day; p < .001) and exhaled CO (13.4 vs. 11.1 ppm; p = .03) between the start and the end

of the 4 week period. Motivation to quit smoking was higher at the week 4 visit than at baseline (5.3 vs. 6.3 on a 10 point scale; $p = .03$). At the end of the study, subjects indicated that quitting menthol cigarettes was difficult (average score = 7.2 on a 10 point scale) but that they were supportive of banning menthol (average score = 7.1). Our finding of substantial support for a ban on menthol cigarettes is consistent with other surveys^{16, 18} and is important data since broadening support for a menthol cigarette ban among current users of menthol cigarettes would likely ease passage of such regulations. The current study would expand on these data to determine if these changes in smoking, motivation to quit smoking, and other measures assessed are either enhanced or undermined by the availability of menthol flavored e-cigarettes. This study will also provide information regarding the level of support among menthol flavored cigarette smokers of banning menthol flavoring across tobacco products.

2.2.2 Experience using an experimental marketplace to evaluate smoker product preferences: [name] conducted a study utilizing an experimental marketplace similar to the one proposed in this project. The goal of the study was to determine the pattern of tobacco use and levels of biomarker exposure when smokers were switched to very low nicotine content (VLNC) cigarettes and had access to alternative nicotine delivery systems.¹⁹ Similar to the proposed study, smokers were randomized to one of three experimental marketplace conditions (i.e., access to combustible and non-combustible products, access to only non-combustible products, and a control normal nicotine content cigarette condition) and were provided a set number of credits which could be used to obtain available products. The study found significant differences in tobacco product use among the three experimental conditions (with greater number of participants in the VLNC condition using alternative products and with higher rate of quit attempts) demonstrating that the experimental marketplace approach was feasible and was acceptable to smokers. The proposed project will evaluate the feasibility of using this approach to study effects of flavorants on tobacco product use.

2.3 *Existing Literature:* Studies have found that when cigarette smokers are provided e-cigarettes to use ad libitum, the number of cigarettes smoked decreases substantially. For example, two studies in which cigarette smokers not interested in quitting were provided e-cigarettes for a 24 week period and asked to use them ad libitum found an overall 80% reduction in median cigarettes per day with 23% - 36% of smokers quitting cigarettes entirely.^{20, 21} Similar results were seen in another study in which smokers were given e-cigarettes that they could use ad libitum over a 2 month period while continuing to smoke.²² All of these studies used tobacco flavored (i.e., non-menthol flavored) products and therefore effects of menthol were not assessed. Studies looking at the effects of e-cigarettes on craving and withdrawal symptoms have found that these products significantly decrease craving and withdrawal symptom severity but most of these studies do not specifically assess menthol flavored products.²²⁻²⁷

Studies that have specifically examined menthol flavoring in e-cigarettes include a study in which African American menthol smokers could select using either menthol or tobacco flavored e-cigarettes (or nicotine gum) for a two week quit

attempt. This study found that 74% selected menthol flavored e-cigarettes.²⁸ A study designed specifically to examine the role of flavor on smoking patterns asked smokers to abstain from cigarettes and only use an assigned flavor of e-cigarettes. This study found that those assigned to menthol flavored e-cigarettes had the largest decrease in number of cigarettes smoked relative to those assigned to tobacco, cherry, or chocolate flavored e-cigarettes.¹³ In an additional cross-over study, twenty non-treatment seeking smokers used menthol and tobacco flavored e-cigarettes, each for 7 – 10 days and completed on their last day of e-cigarettes use, a laboratory session at which they used their assigned product for 5 minutes. In female smokers who used their non-preferred flavor (i.e., menthol smokers using non-menthol e-cigarettes and vice versa), nicotine concentrations were lower and the e-cigarette was rated as less likeable than when using their preferred flavor with no such differences found in men.²⁹ These studies suggest that menthol cigarette smokers prefer menthol flavored e-cigarettes, that menthol flavored e-cigarettes have the potential to decrease smoking to a greater extent than other e-cigarette flavors and that there may be sex differences in response to menthol flavoring in e-cigarettes. The current study will build on this research by providing preliminary data into how availability of e-cigarettes affects cigarette smoking and if these effects are moderated by the availability of menthol flavored cigarettes and / or e-cigarettes.

3.0 Study Endpoints/Events/Outcomes

3.1 Primary Endpoint/Event/Outcome: The primary outcome is the amount of each tobacco product used per week as recorded on their tobacco use surveys.

3.2 Secondary Endpoint(s)/Event(s)/Outcome(s): Secondary outcomes measured at each visit include how much of each product is obtained from the experimental marketplace, motivation and self-efficacy to quit smoking cigarettes and to quit all tobacco product use, number of quit attempts, severity of craving and withdrawal symptoms, and exhaled carbon monoxide concentrations. Support for a menthol ban and urinary cotinine concentrations will be assessed at baseline and at week 6.

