5.2.2 Baseline Visit (i.e., week 0): At the baseline visit, urine will be collected from which baseline urinary cotinine concentrations will be measured. Exhaled CO will be measured from a breath sample. Tobacco use behavior subsequent to the screening visit will be determined as will subjects' level of craving, withdrawal, motivation and self-efficacy to quit smoking and support for a ban on a variety of menthol containing tobacco products. Degree of nicotine dependence will be assessed using the Fagerstrom Test for Nicotine Dependence.³⁰ Subjects will be informed which products are available in the marketplace that they have been randomized to and will be allowed to handle each of the products and examine the packaging that each normally comes in.

Subject will be given credits at each visit that can be exchanged for products in their marketplace. All products will be discounted to approximately 66% of the retail market value (similar to the study summarized in preliminary data) in order to discourage subjects from purchasing products outside the marketplace and also prevent hoarding credits for payment at the end of the study. The credit amount will be calculated in order to allow on average a 1 pack/day smoker to replace all of their tobacco products based on normal usage patterns (e.g., for example, one cartridge of Vuse lasts about as long as one pack of cigarette). In order to discourage subjects obtaining more products than they need, any credits not used at each visit can be banked and used at later visits or converted to monetary payment at the end of the study. Subjects will be informed that they can obtain any amount or type of product up to the value of current and banked credits and will be provided with the packaging that normally accompanies these products. Instructions for product use will be primarily limited to what is on the packaging so as to more accurately simulate natural marketplace conditions; however subjects can ask questions about the products to which accurate answers will be provided. While subjects will be encouraged to obtain all tobacco products they use from the experimental marketplace, no penalties will be levied for outside purchases in order to encourage truthful reports of noncompliance.

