5.2.3 Evaluation Visits (3 visits occurring at 2 week intervals). Subsequent to the baseline visit, subjects will be evaluated at 3 visits occurring at two week intervals (i.e., at approximately 2, 4 and 6 weeks after the baseline visit). To each visit, subjects will be asked to bring back any unused product as well as all used and unused e-cigarette cartridges or e-fluid vials. The cartridges and vials will be weighed prior to distribution and after use to determine the extent to which they were used. Participants will be allowed to keep any of the unused products so as to not discourage them from bringing back unused product.

At each visit, exhaled carbon monoxide concentrations will be measured and subjects will complete questionnaires assessing various aspects of smoking behavior including craving, withdrawal symptoms and motivation to quit smoking. Questionnaires assessing how they rate the effects of the products they are using and their perceived health risks of using these products will also be assessed. A food diary asking primarily about dietary menthol will be completed to determine if dietary intake changes occur if menthol in tobacco products is no longer available. Level of support for a ban on a variety of menthol containing tobacco products will be evaluated at the baseline and week 6 visits.

Additionally, at the week 6 visit urine will be collected in order to measure cotinine concentrations. At each visit (except for the week 6 visit), subjects will again have the opportunity to obtain additional products for the subsequent 2 weeks using their available credits. They may choose to obtain any of the available products in their marketplace and are not limited to products that they had previously chosen.

5.3 Individually Identifiable Health Information: All information is collected directly from subjects (i.e., medical records will not be requested) and this is not a treatment study. The data being collected therefore does not meet the definition of PHI.

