16.0 Data Management

16.1 Data Analysis Plan: Means (arithmetic or geometric for log-transformed variables) and their corresponding confidence intervals will be calculated for each study condition. Results will also be tabulated separately for men and women. A linear mixed model will be fit for each outcome variable, with fixed categorical effects of group, time, and their interaction, and random subject effects to account for correlation among repeated measurements on the same subject. We expect randomization to balance groups with respect to important baseline covariates such as cigarettes smoked per day and degree of nicotine dependence; however, we will check this assumption using ANOVA and consider adjustment for imbalanced factors. Exploratory modeling of gender and race / ethnicity effects will also be performed. Model contrasts will be used to evaluate the hypotheses of the two aims, primarily that cigarettes smoked will be lower and e-cigarette use higher when menthol e-cigarettes are available (Aim 1: conditions A and C compared to B), and that these effects will be larger when menthol cigarettes are unavailable (Aim 2: condition A compared to C)

16.2 Power Analysis: The main purpose of this project is to provide initial information regarding how banning menthol in either only cigarettes or in both cigarette and e-cigarettes will influence tobacco use patterns so as to better design a subsequent study that more definitively addresses this issue. This study will also provide feasibility information regarding using an experimental marketplace for assessing this question. For this pilot study, we plan on recruiting 60 subjects and anticipate (assuming 10% dropout), that there would be 18 evaluable subjects per group. If there is a large effect, we should be able to detect it as this sample size will provide 80% power for a between-groups time-averaged effect size of 0.8, assuming two-sided alpha=0.05 and within-subject autocorrelation of 0.6.

16.3 Data Integrity: In order to ensure that data entry is correct, data collected on paper questionnaires will be entered twice with the two entries compared and any discrepancies resolved.

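### Product obtained from the marketplace exists only at weeks 0, 2 and 4, all under the assigned condition, so it needs its own time points and contrast in the analysis plan

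*Combined protocol and SAP*

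**What the plan says.** Section 3.2 lists the outcome together with motivation, self-efficacy, quit attempts, craving, withdrawal and exhaled CO: "Secondary outcomes measured at each visit include how much of each product is obtained from the experimental marketplace".

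Section 5.2.2 describes the week 0 visit: "Subjects will be informed which products are available in the marketplace that they have been randomized to". The same section introduces the credits: "Subject will be given credits at each visit that can be exchanged for products in their marketplace".

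Section 5.2.3 covers weeks 2, 4 and 6: "At each visit (except for the week 6 visit), subjects will again have the opportunity to obtain additional products for the subsequent 2 weeks". On leftover product it says that "subjects will be asked to bring back any unused product as well as all used and unused e-cigarette cartridges or e-fluid vials", and then: "Participants will be allowed to keep any of the unused products so as to not discourage them from bringing back unused product". Cartridges and vials are weighed. No count of returned cigarettes, gum or lozenges is stated.

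Section 16.1 gives one model for everything: "A linear mixed model will be fit for each outcome variable, with fixed categorical effects of group, time, and their interaction". The contrasts are A and C against B (Aim 1) and A against C (Aim 2). The section does not say which visits enter, whether week 0 serves as a baseline, or whether the contrasts are taken on group means or on the interaction. Section 16.2 expresses the detectable effect as a difference averaged over time.

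**The concern.** Section 3.2 groups this outcome with measures that behave differently at week 0. For CO, craving, withdrawal and motivation, week 0 comes before any marketplace product has been used, so an arm effect shows up as a change from week 0. For product obtained, the first shopping occasion is week 0 itself, in the assigned marketplace, so the arm effect is already in the first value. At week 6 there is nothing to obtain.

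A single contrast cannot suit both kinds of outcome. An analyst who carries the natural contrast for CO over to purchases would subtract the arm effect from itself. This matters because the pilot is meant to inform a larger study and to test whether the marketplace method is feasible (sections 2.2.2 and 16.2), and purchases are the most direct output of that method.

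**Working it through.** **1. When the outcome exists.**

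| Visit | Assigned marketplace known? | Shopping? | Source |
|---|---|---|---|
| Week 0 | Yes | Yes | 5.2.2 |
| Week 2 | Yes | Yes | 5.2.3 |
| Week 4 | Yes | Yes | 5.2.3 |
| Week 6 | Yes | No | 5.2.3 |

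Shopping at week 0 is inferred from two things: credits are introduced under the baseline visit, and 5.2.3 says that participants may obtain products again at later visits. The result is three values, all after disclosure of the condition.

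**2. The plan's own figure.** Inputs from 16.2: 18 per group, effect 0.8 SD, two-sided alpha 0.05, correlation 0.6. Assume three repeated values and equal correlation between them.

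- Variance of the mean of three values: (1 + 2 × 0.6)/3 = 0.7333, so SD = 0.856.
- Standard error of the difference: 0.856 × √(2/18) = 0.285.
- 0.8/0.285 = 2.80, and 2.80 − 1.96 = 0.84, which gives power 0.800 (normal approximation; 0.777 with the noncentral t).

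The stated 80% is reproduced. Three values could be weeks 2, 4 and 6 for the visit measures or weeks 0, 2 and 4 for purchases. Four values give 0.818, so the figure does not settle which visits are meant.

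**3. What each contrast estimates for purchases.** Assume a constant arm difference D at weeks 0, 2 and 4. Power is for D = 0.8 SD, 18 per group and correlation 0.6.

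| Contrast | Estimate | Power |
|---|---|---|
| Mean of weeks 0, 2, 4 | (D + D + D)/3 = D | 0.800 |
| Mean of weeks 2, 4 only | (D + D)/2 = D | 0.765 |
| Mean of weeks 2, 4 minus week 0 | D − D = 0 | 0.05 (alpha only) |

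The interaction behaves like the last row, since each of its components is a difference between equal quantities: D − D at week 2 and D − D at week 4. If the arm difference is not constant, the change contrast equals (D₂ + D₄)/2 − D₀. It then measures only how far the effect grows after the first shopping trip.

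The second row is unbiased under the constant-D assumption but discards one of the three allocations.

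**4. Adjustment.** Daily surveys start once eligibility is confirmed (5.2.1), and use since screening is established at week 0 (5.2.2), so cigarettes per day before week 0 are available. Adjusting for a covariate with correlation r to the outcome multiplies the residual variance by about 1 − r². The documents give no r, so no size is claimed for this gain.

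**The case against.** The strongest reply is that the plan never states the harmful analysis. Section 16.1 defines no change score and no baseline reference, its contrasts are between conditions, and the only effect measure stated, in 16.2, is averaged over time. Averaged over weeks 0, 2 and 4, that measure recovers D. This stands: the analysis is unspecified, not shown to be wrong. It does not remove the point, because the same wording also permits a contrast that returns zero.

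The phrase in 3.2 could also mean purchases for the intervals 0–2, 2–4 and 4–6 weeks. Those are the same three amounts under other labels. They still include no pre-intervention value, and the plan does not state this reading.

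Three stronger inferences are tempting but unsupported:

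- *Week 6 would be entered as zero and dilute the effect.* Section 5.2.3 says that there is no shopping at week 6. Nothing suggests coding a non-event as zero, and a mixed model needs no value there.
- *Unused stock ought to be subtracted.* The outcome is product obtained, a measure of preference, for which the gross amount is correct. Use is measured separately by the daily surveys (the primary outcome) and, for e-cigarettes, by weighing.
- *Condition C would stockpile menthol cigarettes and exaggerate its difference from A.* Section 5.2.2 lets unspent credits be banked or cashed in, expressly to discourage excess purchases. Participants in A and B can obtain the non-menthol version of their usual brand. The documents give no stockpiling rate and no cash-out rate, so neither the direction nor the size of such a bias can be derived.

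**Conclusion.** The point holds as a needed specification for one secondary outcome. The listing in 3.2 does not match the visit schedule: there are three values, at weeks 0, 2 and 4, with neither a pre-intervention nor a week 6 value. Under a constant arm difference, the possible readings of 16.1 range from the full D (average over the three occasions) to zero (change from week 0, or interaction). The zero is a consequence of one permitted reading, not of a stated analysis. The conclusion rests on the inference that shopping starts at week 0; the figures also rest on a constant D and equal correlations. The primary outcome, which is survey-reported use, and the 80% power figure are unaffected.

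**What to change.** In 3.2, take this outcome out of the list measured at each visit. Define it as the amount of each product obtained at weeks 0, 2 and 4, with no week 6 value.

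In 16.1, add that for this outcome all three occasions are post-randomisation and week 0 is not a baseline. State that the Aim 1 and Aim 2 contrasts are taken on the average (or total) over the three occasions. The model-based average is the easier choice when a visit is missed. Because credits can be banked from one visit to the next, an average or total is also less sensitive to when a purchase is made.

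Prespecify adjustment for mean cigarettes per day from the surveys completed before week 0. At present 16.1 only checks balance by ANOVA and then considers adjustment.

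This costs a few sentences and changes no visit, condition or sample size. The covariate is already collected.

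Optionally, in 5.2.3, count the unused cigarettes, gum and lozenges already brought back at weeks 2, 4 and 6. Amount obtained plus amount carried in, minus amount unused, then gives a check on self-reported use beside the gross figure. The cost is a few minutes per visit. The check depends on complete returns: where unused product is left at home, it overstates the marketplace product used.
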